		5.1 Storage	
		5.2 Dispensing of Study Drug	
		5.3 Return or Destruction of Study Drug	
6	\mathbf{S}	ΓUDY PROCEDURES	13
	6.1	Day 0	13
	6.2	Day 1	
	6.3	DAY 2	
	6.4	DAY 3	
	6.5	SCHEDULE OF EVENTS	
7	S	TATISTICAL PLAN	. 17
	7.1	SAMPLE SIZE DETERMINATION	
	7.2	STATISTICAL METHODS	
	7.3	SUBJECT POPULATION(S) FOR ANALYSIS	. 18
8	\mathbf{S}	AFETY AND ADVERSE EVENTS	. 18
	8.1	Definitions	18

8.2	RECORDING OF ADVERSE EVENTS	20
8.3	REPORTING OF SERIOUS ADVERSE EVENTS AND UNANTICIPATED PROBLEMS	20
8	3.3.1 Sponsor-Investigator reporting: notifying the Mayo IRB	21
8.4	STOPPING RULES	22
8.5	MEDICAL MONITORING	
9 D	DATA HANDLING AND RECORD KEEPING	22
9.1	CONFIDENTIALITY	22
9.2	SOURCE DOCUMENTS	
9.3	CASE REPORT FORMS	
9.4	RECORDS RETENTION	
10 S	STUDY MONITORING, AUDITING, AND INSPECTING	24
10.1	STUDY MONITORING PLAN	24
10.2		
11 E	ETHICAL CONSIDERATIONS	25
12 S	STUDY FINANCES	25
12.1	FUNDING SOURCE	25
13 P	PUBLICATION PLAN	25
	REFERENCES	

List of Abbreviations

LIST OF ABBREVIATIONS

AE Adverse Event/Adverse Experience

CFR Code of Federal Regulations

CRF Case Report Form

DSMB Data and Safety Monitoring Board FDA Food and Drug Administration

GCP Good Clinical Practice

HIPAA Health Insurance Portability and Accountability Act

IB Investigator's Brochure

IND Investigational New Drug Application

IRB Institutional Review Board PHI Protected Health Information

PI Principal Investigator

SAE Serious Adverse Event/Serious Adverse Experience

SOP Standard Operating Procedure

Study Summary

Title	Comparison of F-18 FDG PET CT and PET MRI with C-11 acetate PET CT and PET MRI in the diagnosis of active multiple myeloma disease: a Pilot Study				
Running Title	C-11 acetate vs. FDG with PET/CT and PET/MRI in Myeloma				
Protocol Number	16-007867				
Phase	Pilot study				
Methodology	Prospective observational repeated-measure study design				
Overall Study Duration	12 weeks				
Subject Participation Duration	Approx. 270 minutes, over 2 days, in the nuclear medicine suite.				
Single or Multi-Site	Single				
Objectives	1. Our primary interest is to investigate which tracer and imaging technique combination (FDG PET/MRI, C11 PET/CT, C11 PET/MRI) can detect more clinically significantly MM lesions compared to the standard technique (FDG PET/CT). 2. Secondary Objectives: Evaluate which tracer and imaging technique combination (FDG PET/CT, FDG PET/MRI, C11 PET/CT, C11 PET/MRI) best distinguishes the clinically significant MM lesions from other lesions detected.				
Number of Subjects	10				
Diagnosis and Main Inclusion Criteria	Clinically diagnosed multiple myeloma spectrum disease. Adult patients who are able to provide informed consent.				
Study Product, Dose, Route, Regimen	C-11 acetate, 10 mCi, intravenous injections				
Duration of Administration	Bolus injection				
Reference therapy	F-18 FDG				
Statistical Methodology	Objective 1. Repeated measures ANOVA. Univariate one-way repeated measures ANOVA F-test is used to calculate the sample size. Objective 2. One way repeated measure analysis of variance will be employed to detect if there is any difference among the average scores of detected MM lesion in each technique. When the sample size is 10, a single-group repeated measures analysis of variance with a 0.05 significant level will have 80% power to detect a difference in means across the 4 levels by an effect size of 0.32.				

1 Introduction

This document is a protocol for a human research study. This study will be carried out in accordance with the applicable United States government regulations and Mayo Clinic research policies and procedures.

1.1 Background

This project will study differing radiopharmaceutical and imaging approaches in patients with multiple myeloma spectrum disease. The use of carbon-11 (C-11) acetate as a positron emission tomography (PET) tracer to detect multiple myeloma has shown promise in a small number of recent research publications. The current standard clinical PET tracer being used, F-18 fluorodeoxyglucose (F-18 FDG), has some limitations due to the fact that up to 30% of myelomas do not show increased glucose pathway activity. In these patients, recent reports suggest that exploiting the intracellular acetate pathway rather than the glucose pathway may more reliably detect the presence of active myeloma deposits.

The study would include any consent-able adult patient over the age of 20 who is scheduled for a diagnostic FDG PET/CT scan for evaluation of multiple myeloma (MM) for the following indications: new diagnosis, high risk smoldering MM, relapse as defined by investigator.

Acetate is a key component in cellular reactions which result in the oxidative metabolism (via participation in the citric acid cycle in mitochondria), synthesis of fatty acids (in production of cell membranes), and in nuclear histone acetylation (which regulates gene expression). Cell membrane synthesis and gene expression are both important upregulated functions within cancer cells. Intravenously injected C-11 acetate is a radiopharmaceutical which acts identically to normal non-radioactive C-11 acetate in the body. The radioactivity associated with the acetate metabolic pathways can be imaged with positron emission tomographic devices, revealing and permitting visual differentiation of benign versus cancerous tissue by a radiologist.

Our study also incorporates use of a new FDA-approved hybrid PET/MRI technique. This additional modality will permit a four-way technique comparison combination which has not to date been reported.

1.2 Investigational Agent

The investigational agent for this study C-11 acetate is to be manufactured in the Mayo Clinic Arizona radiochemistry facility.

1.3 Preclinical Data

C-11 acetate has been used safely worldwide in patients with cardiovascular disease and cancer over many years. (1-7). For this study non-pharmacologic doses of C-11 acetate will be administered and should not have metabolic effects.

1.4 Clinical Data to Date

F-18 FDG is a glucose analogue that relies on tumor glucose uptake in order to reveal sites of metabolically active tumor. However, 30% of myelomas, such as the non-secretory type, have relatively low rates of glucose metabolism. (8) Recent work in cell metabolism has revealed that in the hypoxic environment of malignant tumors, glucose metabolism is shunted toward lactate production, necessitating an alternative source of acetylCoA for cell membrane fatty acid production. It is believed that in these hypoxic conditions, the acetate uptake pathway becomes a more important route to cell proliferation via cell membrane fatty acid synthesis (9, 10) and nuclear histone acetylation (important in gene transcription from nuclear DNA). (11) A small number of research studies have reported on the efficacy of C-11 acetate, with Ho et all reporting that the sensitivity / specificity of C-11 acetate PET is superior at 84.6%/100% vs. 57.7%/93.1% for F-18 FDG PET. (7)

On the technology front, combined hybrid PET/MRI devices are now FDA approved for diagnostic imaging. PET MRI may improve detection of diffuse marrow infiltration and thereby improve diagnostic utility of the PET data compared to PET CT. To our knowledge, there have been no published reports on the imaging of C-11 acetate for myeloma with PET MR.

1.5 Dose Rationale

The dose of C-11 acetate selected for use in the study patients is 10-15 mCi (370-555 MBq) based on prior published reports by Ho et al. (7). The tracer must be given intravenously.

1.6 Risks and Benefits

C-11 acetate is otherwise identical to endogenous acetate from the pharmacokinetic standpoint. Therefore the study radiopharmaceutical itself will have no nonphysiological action. The main theoretical risk involves the exposure to the radioactivity associated with the C-11 isotope incorporation. This exposure has been calculated to be lower than the standard tracer used, F-18 FDG.(see calculations). The main imaging risk involves exposure to the x-rays used to produce the CT images. However, the exposure is limited to the same low-dose technique involved in production of standard clinically performed PET/CT. Patients with contraindications to PET/MRI will be excluded (metal foreign body fragments or incompatible implanted metallic medical devices).

2 Study Objectives

Primary Objective:

Our primary interest is to investigate which tracer and imaging technique combination (FDG PET/MRI, C11 PET/CT, C11 PET/MRI) can detect more clinically significantly MM lesions compared to the standard technique (FDG PET/CT).

Secondary Objective:

Evaluate which tracer and imaging technique combination (FDG PET/CT, FDG PET/MRI, C11 PET/CT, C11 PET/MRI) best distinguishes the clinically significant MM lesions from other lesions detected.

3 Study Design

This study will be a prospective, observational repeated-measure study to compare the standard technique of F-18 FDG PET/CT with the study techniques of F-18 FDG PET/MRI, C-11 acetate PET/CT and C-11 acetate PET/MRI in the detection of active multiple myeloma in human patients.

The doses of C-11 acetate will be administered intravenously. F-18 FDG is already an FDA-approved intravenous radiopharmaceutical. We anticipate study duration of 12 weeks, if patient recruitment proceeds as expected.

3.1 General Description

Our investigation is titled *Comparison of F-18 FDG PET CT and PET MRI with C-11 acetate PET CT and PET MRI in the diagnosis of active multiple myeloma disease: a Pilot Study.* This study will be a prospective, observational repeated-measure study to compare the standard technique of F-18 FDG PET/CT with the study techniques of F-18 FDG PET/MRI, C-11 acetate PET/CT and C-11 acetate PET/MRI in the detection of active multiple myeloma in human patients. This pilot study of 10 patients will help guide development of a subsequent future prospective study involving a larger cohort of patients. The doses of C-11 acetate will be administered intravenously. F-18 FDG is already an FDA-approved intravenous radiopharmaceutical. We anticipate study duration of 12 weeks, if patient recruitment proceeds as expected.

Our primary interest is to investigate which tracer and imaging technique combination (FDG PET/MRI, C11 PET/CT, C11 PET/MRI) detects the greatest number of clinically significantly MM lesions compared to the standard technique (FDG PET/CT).

[figure not shown]
Our secondary objective is to evaluate which tracer and imaging technique combination (FDG PET/CT, FDG PET/MRI, C11 PET/CT, C11 PET/MRI) best distinguishes the clinically significant MM lesions from other lesions detected.

3.2 Number of Subjects

Ten subjects who have completed all phases of the protocol are required. In order to ensure this, it may be necessary to screen a small number of additional candidates, perhaps up to 5 total, to ensure we reach our study target of ten complete studies. For example, if an enrolled subject cannot or will not return for the second day of imaging, we will recruit and enroll a replacement subject.

3.3 Duration of Participation

There are a total of 4 visits over approximately 32 days. The first 3 visits will be at the Mayo Clinic Arizona campus. The fourth visit involves a phone call. There is an allowed 14 day window between Day 0 and Day 1. There is an allowed 14 day window between Day 1 and Day 2. There is an allowed 4 day window between Day 2 and Day 3.

3.4 Primary Study Endpoints

Our primary interest is to investigate which tracer and imaging technique combination (FDG PET/MRI, C11 PET/CT, C11 PET/MRI) can detect more clinically significantly MM lesions compared to the standard technique (FDG PET/CT).

3.5 Secondary Study Endpoints

Evaluate which tracer and imaging technique combination (FDG PET/CT, FDG PET/MRI, C11 PET/CT, C11 PET/MRI) best distinguishes the clinically significant MM lesions from other lesions detected.

3.6 Primary Safety Endpoints

Adverse events will be monitored through the vital signs evaluated prior to and after investigational product administration.

3.7 Identification of Source Data

Source data for this study will not be directly collected in the Case Report Form (CRF), but will be captured in supportive documentation (study source documents, EMR).

4 Subject Selection Enrollment and Withdrawal

4.1 Inclusion Criteria

- Patients being staged for multiple myeloma as follows: new diagnosis, high risk smoldering MM, relapsed as defined by investigator
- Patients who have undergone standard of care workup
- Patients > 20 years old.
- 300 pounds or less
- Can provide informed consent
- Scheduled for a clinically indicated F-18 FDG PET scan
- English speaking

4.2 Exclusion Criteria

- Pregnant, breast feeding
- Concurrent active non-MM malignancy
- Contraindication to PET MRI
- Previous Type I or Type II Diabetes mellitus or a fasting blood glucose >150 mg/dl

4.3 Subject Recruitment, Enrollment and Screening

Subjects who are scheduled to undergo F-18 FDG PET/CT myeloma evaluation are identified, informed about this study and, if a potential consenting candidate, referred to our study coordinator by our heme/one myeloma specialists from their clinical practice schedule.

4.4 Early Withdrawal of Subjects

If a subject declines to participate in the study after Day 1 of the study, no longer satisfies enrollment criteria or if the patient doesn't return for Day 2 imaging within the study timeframe, they will be withdrawn.

We plan to recruit a replacement subject in the event that a subject withdraws early to maintain the target study number of 10 subjects.

4.4.1 When and How to Withdraw Subjects

Subjects may be withdrawn from the study if consent is withdrawn, if they no longer satisfy enrollment criteria or if they are unable to continue participation due to discomfort.

Data Collection and Follow-up for Withdrawn Subjects:

The F-18 FDG PET/CT and PET/MRI data will be retained for potential future subset analysis regarding PET/CT vs. PET MRI technique. Data collected on study subjects up to the time of withdrawal will remain as part of the study in order for the study to maintain scientifically validity.

Regardless of enrollment status, subject will be contacted per Day 3 tasks for follow-up, and the case reporting documentation will be updated to include this information.

5 Study Drug

5.1 Description

Sodium Acetate C11 Injection is a positron emitting radiopharmaceutical that is used for diagnostic purposes in conjunction with positron emission tomography (PET) imaging. Carbon 11 is a cyclotron produced radionuclide that decays to Boron 11 by positron emission and has a physical half-life of 20.4 minutes.

Sodium Acetate C11 Injection is provided as a ready to use sterile, pyrogen free, clear and colorless solution.

5.2 Treatment Regimen

C11 Acetate will be injected twice for this study on the same day. Route of administration is intravenous. Dose of each injection will be 10 mCi (370 MBq). Acceptable range 5 mCi – 20 mCi.

5.3 Preparation and Administration of Study Drug

Sodium Acetate C11 Injection is prepared on site at the Mayo Clinic PET Radiochemistry Facility in Phoenix, AZ.

Due to radiation concerns, all the chemistry takes place in a fully automated chemical synthesizer located inside a 75mm lead-lined hot cell.

Following quality control testing, the drug product is packaged in a 6mL sterile shielded syringe containing approximately 20 mCi.

5.4 Packaging

The drug product is packaged in a 6mL sterile syringe containing approximately 20 mCi of radioactivity. It is placed inside a lead syringe shield and labeled with the date, batch number, radioactive assay, and drug product name. It is then placed inside a specially designed tungsten lined pneumatic tube capsule and sent to the PET imaging suite.

5.5 Receiving, Storage, Dispensing and Return

5.5.1 Storage

Sodium Acetate C 11 Injection should be stored at 25°C (77°F); excursions permitted to 15 to 30°C (59 to 86°F) (see USP Controlled Room Temperature). The solution should be used within 60 minutes of the end of synthesis calibration time.

5.5.2 Dispensing of Study Drug

Sodium Acetate C11 is made on the day it is used. Each dose is injected in its entirety.

5.5.3 Return or Destruction of Study Drug

After injection of the Sodium Acetate C11 the syringe is assayed for residual radioactivity, to be used in calculation of the precise injected dose. The syringe is then disposed of in the radioactive container.

6 Study Procedures

6.1 Day 0

Informed consent discussion held with subject by research coordinator and consent form signed. Women of child bearing potential are required to have a serum pregnancy test. Women who are surgically sterile and/or greater than or equal to 12 months post-menopausal are not considered as child bearing potential.

Remind patient of overnight fast after 11 pm, except plain water. Review eligibility criteria to confirm all inclusion criteria are met and no exclusion criteria are met.

6.2 Day 1

- 1. Vital signs (sitting blood pressure, heart rate, respiratory rate, temperature) and fingerstick blood glucose are measured by the radiology nurse, who records the results on the source document.
- 2. Investigator MD to see patient, review vital signs and in lay language discuss study objectives, explain the imaging procedures, answer questions. MD signs and dates the source document.
- 3. Subject is brought to the injection room and the radiopharmaceutical is infused intravenously.
- 4. Subject is brought to relax room for one-hour F-18 FDG uptake period. Subject is instructed to remain at rest in the reclining chair, refrain from talking, chewing gum, or getting out of the chair for non-urgent reasons.
- 5. Subject is brought into the PET/CT imaging suite, placed on the scanner table, and imaging carried out.
- 6. Immediately following the PET/CT scan, the subject is brought to the PET/MRI suite and imaging carried out.
- 7. At the completion of the PET/MRI, the patient is brought back to the interview or relax room and vital signs (sitting blood pressure, heart rate, respiratory rate, temperature) are re-checked by the radiology nurse, with the research coordinator recording the results.
- 8. Investigator MD is called by research coordinator to perform post-procedure vital sign review, interview the patient and answer any questions.
- 9. Subject is discharged with instructions for overnight fast except for plain water, beginning at 11 pm.
- 10. Research coordinator places all study data forms in the study binder.

6.3 Day 2

- 1. Vital signs (sitting blood pressure, heart rate, respiratory rate, temperature) and fingerstick blood glucose are measured by the radiology nurse, and the results are recorded on the source document provided by the research coordinator.
- 2. Investigator MD to see patient, review vital signs and in lay language discuss study objectives, explain the imaging procedures, answer questions. MD signs and dates source document.
- 3. Subject is brought to the injection room and the radiopharmaceutical is infused intravenously.
- 4. Subject is immediately brought to the scan room, positioned on the scanning table, and at ten minutes post-injection, PET/CT performed.
- 5. Immediately following the PET/CT scan, the subject is brought to the relax room for a 60 minute wait at rest in the reclining chair.
- 6. After 60 minutes, the subject is brought to the injection room for the second C-11 acetate injection. (NOTE: If the second run of C-11 acetate fails quality control testing, steps 7-11 of the protocol would be postponed until the next day, or within one week).
- 7. Subject is immediately brought to the scan room, positioned on the scanning table, and at ten minutes post-injection, PET/MRI performed.
- 8. At the completion of the PET/MRI, the patient is brought back to the interview or relax room and vital signs (sitting blood pressure, heart rate, respiratory rate, temperature) are re-checked by the radiology nurse, who records the results on the source document provided by the research coordinator.
- 9. Investigator MD is called by research coordinator to perform post-procedure vital sign review, interview the patient and answer any questions. MD signs and dates the source document.
- 10. Subject is discharged.
- 11. Research coordinator places all study data forms in the study binder.

6.4 Day 3

- 1. Research coordinator calls patient to ask if patient has experienced fever, shortness of breath, palpitations, headache or other symptoms. If any of the above have been experienced, investigator MD is immediately notified. Subject is asked about impressions of the experience and whether they believe any additional comfort measures could have been taken.
- 2. Investigator MD is notified of results by the research coordinator. MD signs and dates source document.
- 3. All pre-data analysis study data forms and consent are confirmed intact and in the study binder. Binder is kept in a secured file cabinet in the research coordinators office.

Imaging Techniques

PET/CT: Standard clinical Mayo Clinic whole-body PET/CT acquisition protocol.

PET/MR: PET/MRI myeloma acquisition study protocol:

	t inycloma acquisition study protocol.
Whole Body	
Station 1	
Station 2	
Station 3	
Station 4	
PET Task W	/hole Body
Bed 1 3:0	00
MRAC	1
AX LA	VA-Flex 1
Bed 2 4:	00
MRAC 2	
AX LAV	A-Flex 2
Bed 3 4:	00
MRAC 3	
AX LAV	A-Flex 3
Bed 4 3:	:00
MRAC 4	
AX LAV	A-Flex 4
Bed 5	3:00
MRAC	5
AX LAV	VA-Flex 5
Bed 6 3	:00
MRAC	6
AX LAV	VA-Flex 6
Bed 7 3	3:00
MRAC	7
AX LAV	VA-Flex 7

Comfort Modification: may remove body coils when acquisition of that area is complete, only if needed to keep the subject comfortable.

Schedule of Events 6.5

Study Activity	Day 0	Day 1 °	Day 2 ^f	Day 3 g
Informed consent	X			
History (confirm myeloma spectrum diagnosis). Record result on source document.	X			
Chart information recorded on study source document (height, weight, diabetic, pregnancy and breast feeding status, bone marrow biopsy (if obtained) %, beta-2-microglobulin level (if obtained).	X			
Vital signs prior to and following imaging sessions recorded on source document (sitting blood pressure, respiratory rate, temperature, heart rate)		X	X	
Finger-stick blood glucose prior to imaging		X	X	
CBC ^b , CMP ^c , SPEP ^d , Immunoglobulins, Serum free light chains. Within 4 weeks of study. Obtained as routine clinical tests, not research. Study coordinator will take data from EMR to enter on source/CRF.	X			
Pregnancy test (serum), if applicable ^a	X			
Adverse event evaluation. Results recorded on source document.		X	X	X
PET scans		X	X	
Follow-up call re: adverse events. Result recorded on source document.				X

^a Women of child bearing potential are required to have a serum pregnancy test. Women who are surgically sterile and/or greater than or equal to 12 months post-menopausal are not considered as child bearing potential. Pregnant women will not be allowed to participate in this study ^b CBC (complete blood count); red blood cells (RBCs), white blood cells (WBCs), platelets (PLTs), hemoglobin (Hgb), RBC

indices, and WBC differential

^c CMP (Comprehensive Metabolic Panel; if available, but not required to participate); Glucose, Calcium, Proteins, Albumin, Total Protein, Sodium, Potassium, CO2 (carbon dioxide, bicarbonate), Chloride, BUN (blood urea nitrogen), Creatinine, ALP (alkaline phosphatase), ALT (alanine amino transferase), AST (aspartate amino transferase), Bilirubin d Serum Protein Electrophoresis

^e Day 1 visit to occur within 14 days of Day 0 visit

f Day 2 visit to occur within 14 days of Day 1 visit

g Day 3 visit to occur within 4 days of Day 2 visit

7 Statistical Plan

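### Section 6.3 lists no vital signs between the two Day 2 C-11 acetate injections, and its failed-run note, if followed as written, also postpones the post-dose check

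*Combined protocol and SAP*

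**What the plan says.** Section 5.2 (Treatment Regimen) sets two doses: "C11 Acetate will be injected twice for this study on the same day". Section 3.6 (Primary Safety Endpoints) names the safety measure: "Adverse events will be monitored through the vital signs evaluated prior to and after investigational product administration".

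Section 6.3 (Day 2) runs in this order:

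- Steps 1 and 2: vital signs, then the investigator sees the subject.
- Steps 3 and 4: injection 1, with PET/CT ten minutes later.
- Step 5: "the subject is brought to the relax room for a 60 minute wait at rest in the reclining chair".
- Step 6: "After 60 minutes, the subject is brought to the injection room for the second C-11 acetate injection".
- Step 7: PET/MRI ten minutes after injection 2.
- Step 8: after the PET/MRI, "the patient is brought back to the interview or relax room and vital signs" are taken again.
- Step 9: investigator review. Step 10: discharge. Step 11: filing of forms.

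A note to step 6 covers a second run that fails quality control: "steps 7-11 of the protocol would be postponed until the next day, or within one week".

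The Schedule of Events (6.5) has one row asking for vital signs before and after imaging sessions on Days 1 and 2. It does not say whether a session means one scan or the whole day. Section 8.2 requires adverse-event enquiry at every contact, with examination where appropriate.

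**The concern.** The safety measure is built on readings before and after dosing, yet the first of two doses has no post-dose reading of its own before the subject is injected again. Questioning under 8.2 should pick up symptoms. A change without symptoms could pass unrecorded, and a short-lived one could be over by step 8.

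The failed-run note is the clearer gap. The postponed steps include the vital signs (step 8) and the investigator review (step 9). A subject who has already received injection 1 would then have neither listed for that day. The note also does not bring steps 1 and 2 forward to the later day, so the postponed injection would have no listed pre-dose reading.

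What is at stake is the completeness of a simple safety record, and a check before re-exposure. The lesion-count and clarity comparisons do not depend on it.

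**Working it through.** The plan gives no figure to reproduce here. The check is a count of readings against injections, plus the step times.

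**Readings per subject, as listed in 6.3.** Injections: 2 (steps 3 and 6). Vital-sign sets: 2 (steps 1 and 8). Sets between the injections: 0. Over the 10 completers required by 3.2, that is 10 × 2 = 20 sets now and 10 × 3 = 30 with one added.

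**Time from injection 1 to the first listed reading.**

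- Injection 1 to start of PET/CT: 10 min (step 4).
- PET/CT duration: not given; call it T.
- Rest: 60 min (step 5).
- Injection 2 to start of PET/MRI: 10 min (step 7).
- PET/MRI bed time (Imaging Techniques): 3 + 4 + 4 + 3 + 3 + 3 + 3 = 23 min.

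Injection 1 to step 8 is at least 10 + T + 60 + 10 + 23 = 103 + T min. Transfers and scanner set-up would add to this. Step 8 falls at least 10 + 23 = 33 min after injection 2, so it follows both doses.

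Injection 1 to the start of the rest is about 10 + T min. The gain is at least 103 − 10 = 93 min, whatever T is. Assuming T is 10 to 40 min, the first reading moves from at least 113 to 143 min to about 20 to 50 min after injection 1.

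**Room for review.** Assuming 5 min to measure, 60 − 5 = 55 min of the rest remain for the investigator to look at the set.

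**Why the set belongs at the start of the rest.** C-11 "has a physical half-life of 20.4 minutes", and on storage: "The solution should be used within 60 minutes of the end of synthesis calibration time". If a late reading held back a ready dose, the activity lost would be 1 − 0.5^(5/20.4) = 15.6% after 5 min and 1 − 0.5^(10/20.4) = 28.8% after 10 min. An early set avoids this.

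**How often the failed-run note might be used.** The documents give no failure rate. Assuming independent failures at 1%, 5% or 10% per second run, the chance that at least one of 10 subjects is affected is:

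- 1 − 0.99^10 = 9.6%
- 1 − 0.95^10 = 40.1%
- 1 − 0.90^10 = 65.1%

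These are chances that the note is invoked. They are not chances of harm.

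**The case against.** The strongest reply is that this is an optional extra. Steps 1 and 8 bracket the Day 2 dosing as a whole, and 3.6 does not ask for a set per injection. Day 1 likewise has one set before and one after two scans, although with a single injection. Causality in 8.3.1 is graded to the drug, not to a particular dose, and section 7 plans no vital-sign analysis. Section 1.3 describes the doses as below pharmacologic level and reports long safe use. Section 1.6 expects no action beyond normal physiology and names radiation as the main theoretical risk. Adverse-event enquiry on Day 2 and the Day 3 call remain in place. All of this stands, and it limits the point to a modest improvement.

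A second reply is that the step 6 note is shorthand. It also postpones discharge and form filing, and it leaves out step 6, the very injection being delayed. Staff would probably read it as postponing the second scan and take vital signs before the subject leaves, as 6.5 suggests. That is fair. A reader might infer that a subject would go unmonitored for between one day and a week, but that needs a literal reading that also keeps the subject undischarged. What survives is that 6.3 lists no step for the same-day reading, so the wording should be repaired.

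**Conclusion.** The point holds as a modest, low-cost improvement. Section 6.3 lists no reading between the two injections, and its failed-run note, followed as written, moves the only post-dose set and the investigator review to a later day. An early set brings the first reading forward by at least 93 min. That figure rests on the step times alone; the absolute times rest on an assumed PET/CT duration of 10 to 40 min.

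Three stronger readings are not supported:

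- A reader might infer that the protocol breaches its own safety endpoint. It does not, because 3.6 can be met by one reading before and one after the day's dosing.
- A reader might infer that subjects are exposed to a known hazard. The documents name no mechanism for a vital-sign effect.
- A reader might take the 10% to 65% range as evidence of importance. It rests on assumed failure rates and counts use of the note only.

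**What to change.** **Step 5 of 6.3.** On arrival in the relax room, at the start of the 60-minute rest, the radiology nurse takes one vital-sign set and records the clock time. The investigator reviews it during the rest.

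**Step 6 note.** If the second run fails quality control:

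- the step 5 set and an investigator review are completed before discharge that day;
- only the second injection and the PET/MRI, with their post-scan checks, are postponed;
- the pre-dose vital signs and investigator contact of steps 1 and 2 are repeated on the postponed day.

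No threshold for withholding injection 2 is proposed; that stays with the investigator. The set cannot come earlier than about 10 min plus PET/CT after injection 1, so a very early effect could still be missed.

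**Cost.** One extra short set per subject (10 in total), a few minutes of nurse and investigator time, and small edits to 6.3 and the source document. A subject whose second run fails also has the pre-dose set repeated. The room, the rest period and the nurse are already in use, so no visit or waiting time is added to a normal Day 2 and no delay to injection 2 is expected.
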